Novel use of an enhanced fluoroscopic imaging device to reduce radiation exposure and operative time during intramedullary nailing of hip fractures

NCT02856828

Purpose of the Study:

To evaluate the effectiveness of a novel digital image enhancement (DIE) technology called LessRay in reducing the radiation exposure to both the patient and surgical staff during standard intramedullary nail placement for treatment of hip fractures. Secondarily, to evaluate whether the image quality and reproducibility of desired images can be improved with use of the LessRay Device. Finally, to evaluate whether LessRay Device reduces total operative time.

Background & Significance:

Intraoperative exposure to ionizing radiation is a growing concern for the safety of both patient and OR staff[1-12]. Several studies have shown an association between the dose of radiation the surgeon/surgical staff is exposed to and several types of cancers, including thyroid cancer[1, 3, 6, 7]. Efforts to reduce the amount of radiation during fluoroscopic procedures often result in decreased image quality (i.e. “low pulse rate” imaging). LessRay Device is able to digitally enhance images obtained from a C-arm machine using a low-dose pulse setting allowing for reduction in radiation dose while maintaining image quality. Moreover, LessRay Device allows for saving the precise location of the C-arm in space when the desired image is obtained. This allows for easy return to the exact spot where a previous image was taken, rather than taking multiple fluoroscopic images to return to the similar image. This theoretically reduces both the radiation exposure and total operative time. It also aids in evaluating and confirming reductions throughout the case as the surgeon can return to the previously obtained “perfect” or preferred AP/lateral/oblique image precisely.

The DIE system is a standalone computer display system interfaced to a fluoroscope with a video cable and combines the current image with a prior baseline image of the same anatomy. An algorithm provides for digitally enhanced images (higher resolution) using the low dose-pulse setting.

We anticipate that our results will show the LessRay Device provides a way to drastically reduce the amount of radiation exposure to both the patient and surgical staff during routine intertrochanteric hip fracture fixation. Further studies could then be performed in the hopes of reducing radiation exposure during other orthopaedic trauma cases as well.

We are also hopeful that utilizing the “saved” image feature of the technology will significantly reduce overall operative time while not compromising image quality.

Design & Procedures:

This will be a prospective, randomized study. Patients presenting with closed, intertrochanteric hip fractures requiring intramedullary nail placement will be enrolled. Inclusion criteria will include adult, non-pregnant patients. Patient demographics (age, sex, BMI, any previous hip surgery), fracture type, and total radiation dose to the primary and assistant surgeon, as well as surgical tech and the patient will be documented. Primary surgeon characteristics will also be collected, i.e. post-graduate year (PGY), in

order to account for any differences in training level leading to increased OR time and/or radiation usage.

[figure not shown]
Total radiation emission as documented by the C-arm machine will be recorded. The exact radiation dose to the patient, primary and assistant surgeons, and surgical technician will also be monitored with individual dosimeter badges. Total operative time will be documented. Finally, a brief survey will be issued to the primary and assistant surgeons asking the question: "Was the image quality 'poor,' 'satisfactory,' or 'superior.'" They will also be asked to rate the image quality on a scale of 1-10. Responses to these questions for the standard of care (SOC) fluoroscopy vs. DIE will be compared.

All adult patients presenting with a closed intertrochanteric hip fracture requiring intramedullary nailing will be screened for enrollment. The only exclusion criteria for the study will be age <18 years.

Selection of Subjects:

All adult patients presenting with a closed hip fracture requiring intramedullary nailing. The only exclusion criteria for the study will be age <18 years. Consented subjects will be randomized to either standard of care (SOC) fluoroscopy use or the DIE.

A sample size of 25 per group achieves 93.7% power to reject the null hypothesis of equal means when the population mean difference is 500.0 with standard deviations of 650.0 for SOC group and 240.0 for DIE group. The significance level (alpha) of 0.050 is assumed using a two-sided two-sample unequal-variance t-test. Power calculations are based on historical data which demonstrated radiation doses of 1000 ± 650 in the SOC group and 373 ± 240 in the DIE group. The study would have approximately 80% power to show a 400 mRAD difference based on similar assumptions.

Subject Recruitment & Compensation:

Patients will be recruited from trauma population presenting to the Emergency Department who have sustained a closed hip fracture requiring intramedullary nailing.

There will be no compensation for participation in this study.

Consent Process:

Before a subject's participation in the clinical study, the investigator or study staff will be responsible for obtaining written informed consent from the subject after adequate explanation of the aims, methods, anticipated benefits, and potential hazards of the study and before any protocol-specific screening procedures or any investigational products are administered. Consent will take place in private patient rooms and patients and their families will have time to ask any questions and discuss privately. Inpatients will be given the option to keep the consent to consider participation up until their surgery is scheduled to take place.

Subject's Capacity to Give Legally Effective Consent:

Since there are no risks associated with use of the LessRay Device, LARs will be used for this study, since patients will be recruited from a trauma setting and may or may not be able to give legally effective consent.

Study Interventions:

There are no interventions performed in this study other than the normal operative fixation of the hip fracture. The LessRay Device is added to the regular C-Arm fluoroscopy machine.

Risk/Benefit Assessment:

There is no added risk to the patient. There is a theoretical benefit in less radiation exposure and decreased operative time.

Costs to the Subject:

There are no additional costs to the subjects as a result of participation in this study.

Data Analysis & Statistical Considerations:

Data will be presented using standard summary statistics including the sample size, mean, standard deviation, median, inter-quartile range and range for continuous variables and counts with percentages for categorical data.

Radiation exposure and operative time will be compared between the DIE and SOC groups using either the t-test, if normally distributed, or Wilcoxon rank-sum test otherwise. Power calculations assume that the radiation exposure data are approximately normally distributed; however, this will be tested formally using the Kolmogorov-Smirnov test before comparing groups.

Percentages will be compared using the chi-square test or Fisher's exact test (expected cell counts < 5). Analyses will be done using SAS version 9.4 or higher and a $p < 0.05$ will be considered statistically significant.

Data & Safety Monitoring:

Data monitoring will be conducted on a routine basis by the PI and study team as specified below. Since this technology does not involve any risk to the patient other than loss of confidentiality, we do not anticipate any safety issues.

This study represents minimal risk to subjects, and no adverse events are anticipated. Accordingly, safety monitoring will be conducted to the extent that it ensures privacy and confidentiality, as indicated below.

Privacy, Data Storage & Confidentiality:

Any data that is stored in electronic format will be housed in a secure server behind the Duke University Medical Center firewall. Confidentiality of subject data will be ensured by de-identification of subject data. During data collection, subject identifiers and relevant data elements (specified in Section 3) will be recorded. Then, study-specific identification numbers will be assigned to each subject. Prior to dissemination of any

information in this database beyond the DUMC's secure servers or firewall, all identifiers will be stripped from the database and data will only be referenced by the study-specific identification numbers. A master log, which links the study-specific identification number to the study subject, will be generated in Excel. The master log will be stored as stated above, and will be accessible only to study staff. The adequacy of the Research Data Security Plan will be evaluated and approved by the Orthopaedic CRU prior to protocol conduct. Any publications or presentations that result from this research will not identify any subjects individually, and will present data in aggregate form only.

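### BMI is documented but the planned dose comparison does not use it, so any body-size variation in dose stays in the error term: a loss of precision, not a bias

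*Combined protocol and SAP*

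**What the plan says.** Design & Procedures lists what will be documented: "Patient demographics (age, sex, BMI, any previous hip surgery), fracture type, and total radiation dose". The dose is recorded for the surgeons, the surgical technician and the patient. The same section collects surgeon training level so that differences in radiation use can be accounted for, but names no method. It states no such intention for BMI.

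Selection of Subjects describes allocation in one sentence: "Consented subjects will be randomized to either standard of care (SOC) fluoroscopy use or the DIE". No stratification, by BMI or anything else, is described.

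The power paragraph in the same section opens with "A sample size of 25 per group achieves 93.7% power to reject the null hypothesis of equal means". The difference it is based on is 500, and the assumed spread is given as "standard deviations of 650.0 for SOC group and 240.0 for DIE group". It specifies a two-sided t-test with unequal variances at the 5% level. The calculation is unadjusted.

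Data Analysis & Statistical Considerations gives the comparison itself: "Radiation exposure and operative time will be compared between the DIE and SOC groups using either the t-test, if normally distributed, or Wilcoxon rank-sum", with the choice resting on a Kolmogorov-Smirnov test. It contains no regression, analysis of covariance, stratified test or covariate list.

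**The concern.** The outcome is X-ray dose. As a general physical assumption, a larger patient needs more output for an image of the same quality, so BMI is a plausible predictor of dose in both arms. Eligibility does not restrict body size: the only stated exclusion is age under 18. The historical standard-of-care dose is widely spread, at 1000 ± 650.

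If BMI does predict dose, the plan documents a variable that could narrow the confidence interval and then leaves it out of the analysis. With 25 per arm and no described stratification, the arms may also differ in mean BMI by chance. In that particular trial the estimated dose difference would be pushed up or down, and the planned test has no way to correct for it. Precision is at stake, along with how readily the result could be interpreted if the baseline table shows an imbalance.

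**Working it through.** **Inputs from the documents.** n = 25 per arm; SDs 650 (SOC) and 240 (DIE); difference 500, with a second statement for 400; two-sided alpha 0.05; unequal-variance t-test.

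**Assumed input.** The within-arm correlation r between BMI and dose is not in the documents. I use 0.3 and 0.5, with 0 as the case of no relation.

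**1. The plan's own power.**
- SE = sqrt(650²/25 + 240²/25) = sqrt(16,900 + 2,304) = 138.6, with Satterthwaite df = 30.4.
- Noncentral-t power is 93.72% for a difference of 500 (stated 93.7%) and 79.8% for 400 (stated approximately 80%).

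Both figures reproduce.

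**2. What adjustment is worth on the raw scale.** With correlation r in each arm, the slopes per BMI SD are 650r and 240r. A common-slope model with equal arms estimates their average, 445r. Each arm's own slope differs from that average by 205r. The sum of the two residual variances is

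(650² + 240²)(1 − r²) + 2(205r)² = 480,100 − 396,050r².

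Dividing by 480,100 gives a variance factor of 1 − 0.825r².

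| r | Variance factor | Equivalent n per arm (25 / factor) | SE |
|---|---|---|---|
| 0 | 1 | 25 | 138.6 |
| 0.3 | 0.926 | 27.0 | 133.3 |
| 0.5 | 0.794 | 31.5 | 123.5 |

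These values ignore the small loss from estimating the slope.

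**3. Power with that loss included.** Simulation of the common-slope model with HC3 standard errors (8,000 runs per setting):

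| r | Difference 500 | Difference 400 |
|---|---|---|
| Unadjusted (step 1) | 93.7% | 79.8% |
| 0.3 | 94.5% | 80.5% |
| 0.5 | 97.0% | 86.4% |

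At r = 0.3 the gain is under one point. Simulation error near 80% power is about sqrt(0.8 × 0.2 / 8,000) = 0.4 points, so that gain is barely distinguishable from none. At r = 0.5 it is about 3 points for 500 and 7 for 400. If r = 0, adjustment loses about 2 points.

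**4. Chance imbalance in BMI.**
- The standardised difference in mean BMI has SD sqrt(2/25) = 0.283.
- P(|difference| ≥ 0.4 SD) = P(|Z| ≥ 1.414) = 0.157, counting both directions. About 8% of trials have an imbalance of that size that understates the benefit.
- Expected shift in the dose difference = 0.4 × 445r.
  - r = 0.3: 53, which is 11% of 500 and 53/138.6 = 0.39 of the planned SE.
  - r = 0.5: 89, which is 18% of 500 and 89/138.6 = 0.64 of the planned SE.

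**5. Validity of the planned test.** With BMI related to dose and no true difference, the simulated type I error of the unadjusted unequal-variance t-test was 0.0495 at r = 0.3 and 0.0490 at r = 0.5. Both are nominal.

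**The case against.** The strongest reply is that nothing is wrong as written. Randomisation keeps the unadjusted comparison unbiased on average, and its type I error is nominal. The SDs of 650 and 240 appear to be total SDs that already contain any body-size variation, so the power statement needs no correction. Chance imbalance in BMI is one of the sources of variation that the standard error covers. At the full historical difference, 1000 − 373 = 627, unadjusted power is 99.2%, so the trial does not depend on the gain. All of this stands.

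The reply also says that the benefit rests on an r that the documents do not supply, and that at r = 0.3 it is negligible. That stands too. What remains is that a prespecified adjustment for a variable already on the data list costs almost nothing and could give a useful gain if r is nearer 0.5.

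Some stronger readings are tempting, and the documents do not support them:

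- **The dose estimate will be biased.** A particular trial may be shifted by an imbalance, but shifts in the two directions are equally likely.
- **A 0.4 SD imbalance moves the result by 20%.** This comes from applying the root-mean-square SD of 490 to both arms: 0.5 × 0.4 × 490 = 98. It implies a slope of 245 per BMI SD in the DIE arm, more than that arm's whole SD of 240 and so a correlation above 1. Arm-specific slopes give 89.
- **BMI will be available for every patient before surgery.** The protocol says only that it will be documented, without timing or completeness.

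**Conclusion.** The concern holds as a modest improvement in precision. The dose comparison leaves out a documented and plausibly predictive variable, and neither the analysis section nor the described randomisation uses it otherwise. The gain is small at r = 0.3 and worthwhile at r = 0.5, mainly for the smaller difference of 400, where power is thinner. It could be slightly negative if BMI is unrelated to dose.

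The sizes rest on three assumptions: the value of r, the same r in both arms, and a linear relation on the raw dose scale. A reader might infer that the plan is invalid or underpowered for lack of adjustment. The nominal type I error and the reproduced power figures show otherwise.

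**What to change.** In Data Analysis & Statistical Considerations, prespecify that dose is also compared by linear regression on arm and continuous BMI with heteroscedasticity-robust standard errors (for example HC3, given SDs of 650 and 240). Report the adjusted DIE − SOC difference with its 95% CI, keep the planned unadjusted test alongside it, and state which of the two is the main result. Settle this before outcome data are seen: adjusting only after an imbalance has appeared would be post hoc.

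A log-dose model giving a DIE/SOC ratio would suit the nearly equal coefficients of variation (650/1000 = 65% and 240/373 = 64%). It would, however, replace the mean difference on which the sample size was based. If it is wanted, it should be a separate and explicit choice. Which of the recorded dose measures to analyse is likewise a separate question.

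The cost is a sentence or two in the plan and one model in SAS, with no new patients and no new variable. A simple rule for missing BMI is needed, because the protocol does not guarantee complete values in an emergency population. The statistical downside is the loss of about 2 points of power if BMI turns out to be unrelated to dose.

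### Fracture type is recorded but no use of it is stated in randomisation or in the operative-time and dose comparisons; prespecifying it as a covariate is a cheap, possibly small, gain in precision

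*Combined protocol and SAP*

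**What the plan says.** Design & Procedures lists the recorded variables: "Patient demographics (age, sex, BMI, any previous hip surgery), fracture type, and total radiation dose to the primary and assistant surgeon". Fracture type is not named again. Allocation is described in one sentence under Selection of Subjects: "Consented subjects will be randomized to either standard of care (SOC) fluoroscopy use or the DIE". It gives no stratification factor and no method.

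Operative time is the last of the aims in Purpose of the Study ("Finally, to evaluate whether LessRay Device reduces total operative time") and also appears in the title. Its analysis, shared with dose, is in Data Analysis & Statistical Considerations: "Radiation exposure and operative time will be compared between the DIE and SOC groups using either the t-test". The alternative, for data that are not normal, is the Wilcoxon test. Neither test carries a covariate.

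The plan does expect features of the case to affect these outcomes. Surgeon post-graduate year (PGY) is collected in "order to account for any differences in training level leading to increased OR time and/or radiation usage". The analysis section gives no method for that either.

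Both power statements, under Selection of Subjects, concern radiation dose. No SD, target difference or power is given for operative time.

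**The concern.** Fracture type is fixed by the injury, so allocation cannot affect it. It plausibly governs how hard the fracture is to reduce, and hence how long the case takes and how many images are needed. Background & Significance itself names checking the reduction as a step where the device should help. An unadjusted test leaves this variation in the error term, and with 25 per arm the mix of fractures can differ noticeably between arms by chance.

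The fracture mix is also not fully settled. One eligibility wording is narrow ("Patients presenting with closed, intertrochanteric hip fractures requiring intramedullary nail placement will be enrolled"), while Selection of Subjects and Subject Recruitment & Compensation admit any closed hip fracture that needs a nail. The wider reading would make fracture type matter more.

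At stake is the width of the interval for operative time and, to a similar degree, for dose. If no covariate is named in advance, an imbalance noticed later can be dealt with only by post hoc adjustment.

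**Working it through.** **The plan's own figures (dose).** The inputs are 25 per group, SDs of 650 and 240, two-sided alpha of 0.05 and an unequal-variance t-test.
- Standard error = sqrt(650²/25 + 240²/25) = sqrt(16900 + 2304) = 138.6; Satterthwaite df = 30.4.
- Difference of 500: noncentrality 500/138.6 = 3.61, power 93.7% (stated 93.7%).
- Difference of 400: noncentrality 400/138.6 = 2.89, power 79.8% (stated as approximately 80%).

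Both reproduce.

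**Operative time, unadjusted.** No SD is given, so the unit is the total SD of operative time. With 25 per arm and 48 df:
- Standard error = sqrt(2/25) = 0.283 SD.
- 95% CI half-width = 2.011 × 0.283 = 0.57 SD.
- Detectable difference at 80% power (noncentral t) = 0.81 SD.
- Power at a true difference of 0.5 SD = 41%.

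**Operative time, adjusted for a two-level fracture type.** The residual SD becomes sqrt(1 − R²) and the df 47. R², the share of variance that fracture type explains, is an assumption.

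| Assumed R² | Detectable difference, 80% power | Power at 0.81 SD | Power at 0.5 SD | Equivalent sample size, 1/(1 − R²) |
|---|---|---|---|---|
| 0 (unadjusted) | 0.81 SD | 80% | 41% | 1.00 |
| 5% | 0.79 SD | 82% | 43% | 1.05 |
| 10% | 0.77 SD | 84% | 45% | 1.11 |
| 20% | 0.72 SD | 88% | 49% | 1.25 |
| 30% | 0.68 SD | 92% | 54% | 1.43 |

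These figures ignore a small penalty. Chance correlation between arm and fracture type raises the variance of the adjusted estimate by about 1/(1 − 1/49) = 1.02 on average, which would move 0.79 to about 0.80 SD and 0.68 to about 0.68 SD.

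**What such an R² requires.** For prevalence p of the harder type and a difference d in within-level SDs, R² = p(1 − p)d² / (1 + p(1 − p)d²). At p = 0.5, d = 0.5, 0.7, 1.0 and 1.3 give R² of 6%, 11%, 20% and 30%.

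**Chance imbalance.** Take the counts of harder fractures as two independent Binomial(25, p) variables, as under unstratified allocation. A gap of at least 5 of 25 (20 percentage points), in either direction, has probability 16%, 19% or 20% for p = 0.3, 0.4 or 0.5 (assumed). In any one direction it is half that, about 8% to 10%.

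**Shift in the estimate.** With d = 1 within-level SD, a 20-point gap moves the unadjusted difference by 0.20 within-level SD. The total SD is sqrt(1 + p(1 − p)) within-level SDs, so at p = 0.5 the shift is 0.20/sqrt(1.25) = 0.18 total SD. That is 0.18/0.81 = 22% of the detectable difference and 0.18/0.283 = 0.6 of a standard error.

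**The case against.** The strongest reply is that nothing here is wrong. An unadjusted comparison of randomised groups is a legitimate plan, and recording a baseline variable does not oblige anyone to model it. The only factor the protocol undertakes to account for is PGY. This stands, and it is why the point is an improvement and not an error.

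Several further parts of the reply also stand:
- Error variance and chance imbalance are one effect. The 0.57 SD half-width already contains it, so the two must not be added together.
- R², prevalence and the operative-time SD are all absent from the documents. At R² of 5% to 10% the gain is 2 to 4 points of power at 0.81 SD, and at a true 0.5 SD the comparison stays underpowered after adjustment.
- A covariate does not supply the missing power statement for operative time.
- The randomisation method is not described and a figure is not shown, so one can say only that no use of fracture type is stated. Categorical data will be summarised as counts and percentages, so an imbalance would probably be visible.

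A reader might infer that operative time is the result most likely to be missed. The documents do not support that ranking: there is no SD or target difference to rank by, and image quality has no stated power either.

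What the reply does not remove is that the variable is already collected, that the plan itself expects case-level factors to affect OR time and dose, and that a covariate has to be named before the 50 outcomes are seen if it is to be free of selective adjustment.

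**Conclusion.** The point holds as a low-cost improvement in precision. No use of fracture type is stated in randomisation, and the operative-time and dose comparisons are unadjusted. For operative time, adjustment would lower the 80%-power detectable difference from 0.81 SD to between 0.79 and 0.68 SD if fracture type explains 5% to 30% of the variance. That range is assumed, and at its lower end the gain is small. A gap of at least 20 percentage points in fracture mix would arise in 16% to 20% of trials if 30% to 50% of fractures are the harder type. With an effect of 1 within-level SD, such a gap shifts the estimate by at least about 0.18 total SD.

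It would be tempting to conclude that the planned comparison is biased or has an inflated type I error. It does not follow: under valid randomisation imbalance is random, and the standard error allows for it. Nor does the point show that 25 per arm is wrong. That number was set for dose, and both dose power figures reproduce.

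**What to change.** In Data Analysis & Statistical Considerations:
1. Make the operative-time analysis a linear model with terms for arm, a two-level fracture type and PGY. The PGY term also carries out what Design & Procedures says will be accounted for.
2. Fix the outcome scale, raw or log time, in advance. Choosing it from the residuals would be data-dependent, and log time changes the reported effect to a ratio.
3. Define the two levels from the fracture type already recorded, before any outcome data are seen.
4. Report the adjusted difference with its 95% CI, and keep the unadjusted comparison as supportive.
5. Add the same fracture-type term to the dose analysis.

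The two eligibility wordings should be reconciled so that the grouping covers the fractures actually enrolled. Stratifying randomisation by the same two levels is optional and not needed for this fix.

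The cost is SAP wording, one degree of freedom for fracture type and the need to agree the grouping early. The documents give no classification to start from, so that agreement is the real work. No new patients, visits or measurements are required.

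### Surgeon training level is collected so that it can be accounted for, but no stated allocation or analysis method accounts for it

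*Combined protocol and SAP*

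**What the plan says.** All places are in the combined protocol and SAP.

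- **Design & Procedures** states what is collected, "Primary surgeon characteristics will also be collected, i.e. post-graduate year (PGY), in", and the sentence runs on to give the purpose: "order to account for any differences in training level leading to increased OR time and/or radiation usage". This names a prognostic factor, the two outcomes it is expected to affect, and an intention to account for it. A figure follows that sentence and is not shown in the text available.
- **Design & Procedures** and **Selection of Subjects** describe allocation only as "This will be a prospective, randomized study" and "Consented subjects will be randomized to either standard of care (SOC) fluoroscopy use or the DIE". No stratum, block, minimisation factor or surgeon factor is given.
- **Data Analysis & Statistical Considerations** says "Radiation exposure and operative time will be compared between the DIE and SOC groups using either the t-test", with the Wilcoxon rank-sum test as the alternative when data are not normal. On normality, "this will be tested formally using the Kolmogorov-Smirnov test before comparing groups". For categorical data, "Percentages will be compared using the chi-square test" or Fisher's exact test. No covariate, model, stratified test or subgroup appears.
- **The sample-size paragraph** (end of Selection of Subjects) is also for an unadjusted two-sample test: 93.7% power at a difference of 500, and "The study would have approximately 80% power to show a 400 mRAD difference based on similar assumptions".

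**The concern.** The plan gives a reason for collecting PGY and then never uses it. Summary statistics and chi-square or Fisher tests could show whether PGY differs between arms, but showing an imbalance does not account for it in the comparison of radiation or operative time.

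With 25 patients per arm and no stratification, one arm can easily receive noticeably more junior surgeons. If juniors use more radiation or take longer, as the plan itself anticipates, the error can run either way. More juniors in the DIE arm would hide a real reduction, and more in the SOC arm would flatter the device. The trial would then report a result affected by a factor it had identified and recorded, with no agreed way of allowing for it.

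**Working it through.** **1. The plan's own power.** Inputs from the sample-size paragraph: 25 per arm, SDs 650 and 240, two-sided 0.05, unequal-variance t-test.

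- Variances of the means: 650²/25 = 16,900 and 240²/25 = 2,304. SE = √19,204 = 138.58.
- Satterthwaite df = 19,204² / [(16,900² + 2,304²)/24] = 30.4.
- Difference 500: noncentrality 500/138.58 = 3.61, power 93.7%.
- Difference 400: noncentrality 400/138.58 = 2.89, power 79.8%.

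Both stated figures reproduce, and no surgeon term enters them.

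**2. How often surgeons split unevenly.** The documents give no PGY mix, so I assume juniors do 30%, 40% or 50% of cases. A gap of at least 20 points means at least 5 patients out of 25. With two independent binomials, the exact probability is 16.4%, 19.3% and 20.3%, or 8.2%, 9.7% and 10.1% in each direction.

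**3. What a 20-point gap does.** The documents give no training effect, so I assume junior mean dose is *f* times senior mean dose in each arm. Take *f* = 1.5, 40% junior, and arm means 1000 and 600:

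- Senior means are 1000/1.2 = 833.3 and 600/1.2 = 500. Junior excess is 416.7 in SOC and 250 in DIE.
- A gap of 10 points above the average share in one arm and 10 below in the other shifts the observed difference by 0.1 × 416.7 + 0.1 × 250 = 66.7, or 66.7/138.58 = 0.48 SE.
- The expected difference becomes about 333 or 467. The formula in step 1 then gives power of about 64% or 90%.

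**4. Unadjusted against adjusted power.** Simulation with 20,000 trials per case, normal data, arm means 1000 and 600, and SDs 650 and 240 including the PGY part. Welch test against a linear model with arm and a junior/senior term (HC3 robust errors, 47 df). Fixed gaps are 10 v 5, 12 v 7 and 15 v 10 juniors. Ranges cover the three junior shares.

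| Assumed *f* | 20-point gap, more juniors in DIE | 20-point gap, more juniors in SOC | Average over randomisations |
|---|---|---|---|
| 1.0 | – | – | 80% v 78% |
| 1.2 | 73–74% v 77–78% | 85–86% v 76–78% | 80% v 78–79% |
| 1.5 | 64–66% v 81–82% | 91–92% v 80–81% | 80% v 82% |

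**5. Is the assumed effect plausible on this scale?** Share of within-arm variance due to PGY = p(1−p) × (junior excess)² / SD².

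- *f* = 1.5, 40% junior: DIE 0.24 × 250²/240² = 26%; SOC 0.24 × 416.7²/650² = 10%.
- *f* = 2.0: in DIE, 30% junior gives an excess of 600/1.3 = 461.5 and 0.21 × 461.5²/240² = 78%; 50% junior gives an excess of 400 and 0.25 × 400²/240² = 69%.

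A two-fold effect would make training level explain most of the DIE dose variation, so I report no power figures for it. The documents give no SD for operative time, so there is no figure for that outcome.

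**The case against.** The strongest reply is that randomisation already deals with surgeon mix. That is right as far as validity goes. The unadjusted tests are unbiased over repeated randomisations, their standard error allows for chance imbalance, and a null simulation of the Welch test gave an error rate of 5.1%. A reader might infer that the planned comparison is biased or invalid, and the documents do not support that.

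A second reply is that adjustment buys little. At a 1.2-fold effect or less, average power does not rise and may fall by one or two points. When SOC has more juniors, the adjusted test has the lower power. This also stands. The average gain depends on a training effect of about 1.5-fold or more, which the documents neither state nor exclude.

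Three other strong readings fail:

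- That the primary analysis is left open until the data are seen. The analysis section fixes the unadjusted comparison, so a later PGY adjustment would be a visible departure from it. What is not fixed is how PGY would be used.
- That other recorded variables, such as BMI and fracture type, are neglected in the same way. They are listed without any stated analytic purpose.
- That the plan certainly contains no method anywhere. The figure after the PGY sentence cannot be read, so the finding is limited to the visible text. The analysis section, however, is present and does not mention PGY.

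None of this removes the mismatch. Following the plan as written does not do what it says PGY is collected for.

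**Conclusion.** The point holds as a gap between stated purpose and method, not as a validity failure. It should be put right, but its expected effect is modest.

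The size depends on two assumptions that the documents do not supply: the share of cases done by juniors (30–50%) and the junior-to-senior dose ratio (up to 1.5). On those, roughly one trial in five or six has a gap of 20 points or more. In such a trial at 1.5-fold, the unadjusted test either loses about 15 points of power relative to its nominal 80% or gains about 12, according to which arm drew the juniors. The adjusted test stays near 81% in both cases. Its main benefit is therefore a result that depends less on the draw of surgeons. Gain in average power is secondary, and absent if the training effect is small.

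**What to change.** In Data Analysis & Statistical Considerations, prespecify for radiation exposure and for operative time a linear model with treatment arm and one junior/senior PGY term.

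- Fix the PGY cut-point before enrolment, and count surgeons no longer in training as senior.
- Keep the original scale with robust standard errors and name the estimator, so that the estimate remains the mean difference on which the sample size rests.
- Use the PGY of the surgeon assigned before the allocation is known, so that the covariate cannot be affected by the arm.
- Report the planned unadjusted test alongside. Whether to keep the Kolmogorov-Smirnov choice between t-test and Wilcoxon is a separate question.
- Stratifying randomisation by junior/senior is optional.

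The cost is one model sentence, one recording step (the surgeon logged before allocation, since the plan gives no timing for PGY) and one degree of freedom. If PGY has little or no effect, about one to two points of power are lost. That loss depends on the estimator: with HC2 instead of HC3, power when PGY explains nothing is 79.9% and not 78%, but type I error rises to about 5.4%. In trials where SOC happens to have more juniors, adjusted power is below unadjusted power. Deleting the stated purpose would also end the mismatch, but would give no protection against an uneven split.
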